STUDY PROTOCOL

Validation study on RENEW's Aingeal at KK Women's and Children's Hospital

CRIB NUMBER:

2018/2223

PROTOCOLL VERSION: 1.0

PROTOCOL DATE: 3 April 2018

PRINCIPAL INVESTIGATOR:

[name] [name], Associate Consultant, Department of Paediatrics, KK Women's and Children's Hospital (KKH)

A/[name] [name], Senior Consultant, Department of Women's Anaesthesia, KK Women's and Children's Hospital (KKH)

INTRODUCTION

RENEW's Surveillance Monitoring system is made up of two main components: a patient-worn wireless vital signs monitor (Aingeal) that transmits data over Wi-Fi to a central station software platform (Surveillance Station).

The Aingeal device measures single lead ECG, heart rate, respiration waveform and rate, and skin temperature. A snapshot of data is transmitted by the devices intermittently to the Surveillance Station, enabling vital signs trends to be plotted. If any heart, respiration rate or skin temperature values move outside of pre-defined high and low limits (individually set for each patient) an alert is raised. ECG arrhythmia detection algorithms automatically record and send ECG data if the patient is suspected to be experiencing an arrhythmia event (Asystole, Ventricular Fibrillation, Tachycardia or Bradycardia).

This proposal describes the evaluation of RENEW's Aingeal device within a paediatric out-patient setting in KK Women's and Children's Hospital ("KKH"), the main tertiary women and children hospital in Singapore.

In the paediatric population, assessment of RENEW's Aingeal device will include the accuracy of the device at deriving heart rate from single lead ECG and at deriving respiratory rate when compared against a commonly used vital signs monitor.

User acceptance of Aingeal and the Surveillance System will be considered within paediatric settings.

AIMS & OBJECTIVES

The aims of the study are:

- To examine the validity of vital signs recorded from paediatric patients (aged between 3 and 17 years) using the Aingeal device
- To determine user acceptance of Aingeal and the Surveillance system

The study will determine whether:

- 1. Heart rates calculated by the Aingeal device during paediatric patient monitoring are within clinically acceptable accuracy ranges
- 2. Respiration rates calculated by the Aingeal device during paediatric patient monitoring are comparable with respiration rates recorded using a portable bedside End Tidal Carbon Dioxide (ETCO₂) monitor.
- 3. The Aingeal device and Surveillance system are acceptable to Healthcare Professionals (HCPs), to paediatric patients, and to paediatric patients' parents or guardian.

STUDY DESIGN

Paediatric Out-patient Population

The Surveillance System will be installed in a paediatric outpatient clinic at KKH. A standalone Wi-Fi network will be set up to facilitate system use for the purposes of the study. Children attending the clinic aged between 3 and 17 years old will be invited to participate. Written consent from the child's parents or guardian will be obtained prior to participation.

Subsequent to obtaining consent, trained personnel will confirm the child's eligibility with their parent or guardian against the following inclusion and exclusion criteria:

Inclusion Criteria

- ✓ Male or female paediatric patients, aged between 3 and 17 years
- ✓ Patients attending outpatient care at KKH Women's and Children's Hospital, Singapore

Exclusion Criteria

- * Patients with active, implantable devices (such as a pacemaker or ICD)
- * Patients with any skin condition or injury affecting the electrode placement site
- **x** Patients that are pregnant
- * Those patients who, in the opinion of the outpatient clinic staff, are not suitable to participate.

Eligible and willing patients will be set up with an Aingeal electrode and device and Medtronic's Capnostream 35 portable respiratory cannula.

Recording of vital signs will begin at resting phase with the study subjects seated comfortably for 10 minutes. Younger children may be seated on the caregiver's or parents' lap. After the resting phase, the child will be asked to take a short walk around the clinic for 5 minutes. Younger children may be offered the playground instead.

Information on age, height, weight, sex and medical history will be collected from the patients' medical notes or reported by the patient's parent or guardian. At the completion of vital signs recording, feedback from the child and their parents or guardian will be obtained using self-reported questionnaires (Appendix 1).

Patient Identification

A patient enrolment log will be maintained at each investigational site. This enrolment log will link the identifiable patient to a study patient number which will be used on all study data.

Withdrawal and Discontinuation

All patients will have the right to withdraw their participation from the study at any time. Withdrawal will not affect their routine medical care. Patients may be withdrawn if it is thought to be in their best interests. The reason for withdrawal of any patient will be documented and any data gained up to the point of withdrawal may be used in analyses.

DATA ANALYSIS AND STATISTICAL METHODS

Paediatric Out-patient Population

Paediatric patients will be monitored simultaneously using the Aingeal and Capnostream devices for fifteen minutes over two phases (ten minutes at rest and five minutes during walking or playing). Before data collection commences, the time on the Surveillance Station will be verified against the time on the Capnostream device to ensure that respiratory data can be paired as closely as possible.

Heart Rate Comparison

Each of the ECG waveforms recorded by the Aingeal device will have heart rate calculated manually by a trained reviewer that has been blinded to the heart rate derived by the Aingeal device to minimise bias. Ten subjects will provide approximately 100 minutes (or 2 hours) of Aingeal data and approximately 100 heart rates. Both sets of heart rates will be compared using the approach of Bland Altman [1,2].

Respiratory Rate Comparison

The Aingeal device averages respiration rate over a 30 second window (or a period of 10 breaths, whichever is shorter). The respiration rate is updated each minute at the Surveillance Station. The Capnostream device stores data at resolution of 1 sample per second.

As a result there will be many more data points from the Capnostream device than from the Aingeal device over the same observation period. Ten subjects will provide approximately 100 minutes (or 2 hours) of Aingeal data and approximately 100 respiration rates. Both sets of respiratory rates will be compared using the approach of Bland Altman. Datasets will be stratified by age group as described in Table 1.

A total sample of 10 paediatric outpatients stratified by the age groups of 3 to 5 years old, 6 to 9 years old, 10 to 14 years old and 15 to 17 years old is estimated to provide an accuracy of 5% for respiratory rate, with estimated differences ranging from 0.7 to 1.25 breaths. The sample estimation is calculated based on a minimum of 8 repeated measures per child, having accounted for 20% attrition rate and 20% data loss due to signal loss, noise or time discrepancies.

Bland Altman Analysis

The heart and respiration rate counts from each measurement method will be compared against each other in a pair-wise manner using the approach of Bland & Altman. For each parameter, this involves plotting the difference in the counts against the mean of the two absolute counts. The 95% and 99% limits of agreement, equivalent to 2 times standard deviation (sd) and 3 sd will be plotted. This process will be repeated for each portion of the test (at rest and during activity) and for each age group (3 to 5 years old, 6 to 9 years old, 10 to 14 years old and 15 to 17 years old) for heart rate and respiration rate. Adjustments for age and sex will be considered.

Feedback and Demographic Analysis

Summaries of patient, parent and HCP acceptability, demographics and medical history will be produced. In general, categorical data will be summarised using frequency counts and percentages, and continuous data will be summarised using means, standard deviations, minimums, medians and maximums.

RENEW'S AINGEAL PROCESS REQUIREMENTS

A. Application and Registration

No	Step by Step Application
1	Add patient to Central (Surveillance) Station.
2	Assign Aingeal Device to patient. (Pair the RENEW's Aingeal Device identifier code with Subject ID on the Surveillance Station and on the Patient Log)
3	Thoroughly clean the skin using alcohol wipes. Poor skin prep may result in poor signal quality.
4	Apply electrodes: Position the electrodes as shown in the figures below. RENEW's Aingeal Device should be placed on the left chest, just left of the centre of the sternum and below the collar bone. The right chest electrode should be placed just right of the centre of the sternum and below the collar bone. Place the electrode on the left side of the patient's body at the 7th rib and on the midline.
5	Connect device & start-up: Turn on RENEW's Aingeal device by pressing the "ON" Button. Check that the device beeps, that the Wi-Fi LED changes from orange to green, and that the Leads LED changes from blue to unlit.
6	Start Monitoring Patients on RENEW's Surveillance Station. Validate waveforms.
7	Check alarm limits.

[figure not shown]

Fig. A. Aingeal Device on adult

B. Data Collection and Validation

The RENEW's Aingeal is a wearable wireless device that measures single lead ECG and impedance pneumography waveforms to derive heart and respiration rates. Skin temperature is measured via a thermistor on the electrode patch. Every minute these parameters and a 25 second snapshot of waveform data are transmitted to the Surveillance Station over Wi-Fi.

The RENEW's Aingeal will be attached onto the Subjects for continuous monitoring during the Study.

- i. The Subjects will each be identified by a unique Subject ID assigned at time of recruitment and a Device ID using an agreed format.
- ii. Raw vital signs data ie. Readings, will be extracted from Surveillance System and provided to KKH research team for further study data mapping and analysis.

- iii. Sampling Rate will be derived using a data averaging method over a period of 60 seconds for the Capnostream data output. KKH requires all raw data points, in additional to per minute.
- iv. KKH will extract the averaging data points for further data processing and mapping against the Subject's demographics; e.g age, gender, height, weight etc.

For first week of the trial, Renew is required to extract the daily data files onsite and provide to KKH. This is to ensure that the setup is working well and correct data is collected and verified. There is no contact between the participants and the representative from the study sponsor. Also, the patient's details will not be keyed into the system as we will only put participant's subject ID number, which will not allow sponsor to identify the patients. Removal and De-Registration

No	Step by Step Application
1	Turn off the RENEW's Aingeal by pressing and holding the "OFF" Button on the RENEW's Aingeal until the green LED is unlit.
2	Remove the RENEW's Aingeal gently from the Subject
3	Slowly and carefully remove the electrodes from the Subject
4	The subject can be discharged from the Surveillance Station after data collection has completed and all required data is collected.
5	Dispose the electrodes appropriately into designated bins.

C. Training Plan

The training program is designed to provide the relevant study team members with sufficient knowledge and skills to configure and use the RENEW Surveillance System. The program will comprise of interactive instructor led clinical demonstration.

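### The child and parent questionnaire is tied to the end of recording, with no provision for families who stop early, so the acceptability and skin-irritation results may be biased, plausibly upward

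*Combined protocol and SAP*

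**What the plan says.** Objective 3 asks whether "The Aingeal device and Surveillance system are acceptable to Healthcare Professionals (HCPs), to paediatric patients, and to paediatric patients' parents or guardian". For children and parents, the evidence is the participant questionnaire in Appendix 1. Its six five-point items include comfort, daily activities and skin irritation.

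The Study Design section (Paediatric Out-patient Population) sets out 10 minutes at rest and then 5 minutes of walking or play. It then places the form: "At the completion of vital signs recording, feedback from the child and their parents or guardian will be obtained using self-reported questionnaires". No other time is given.

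Early stopping is covered in Withdrawal and Discontinuation. Any child may leave at any time or be withdrawn in their best interests, the reason is documented, and "any data gained up to the point of withdrawal may be used in analyses". That section does not mention a questionnaire.

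The Respiratory Rate Comparison section gives the sample size as "having accounted for 20% attrition rate and 20% data loss due to signal loss, noise or time discrepancies". Causes of attrition are not stated.

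The Feedback and Demographic Analysis section says that "Summaries of patient, parent and HCP acceptability, demographics and medical history will be produced", using counts and percentages for categorical items. It gives no denominator, no rule for missing forms, and no link to the withdrawal reasons.

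**The concern.** Followed literally, the text gives the form only to families who reach the end of the 15-minute sequence. The permission to use data gained before withdrawal does not help, because the form has not been handed out by then.

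The visit is one short session, so loss through missed follow-up visits hardly arises. Children as young as 3 wear chest electrodes and a nasal cannula. Dislike of the equipment is a plausible reason to stop early, and it is what objective 3 is meant to detect. If that is why children stop, the comfort and skin answers would come from the children who tolerated the device, and the summary would look better than the experience of everyone fitted with it. With about ten children, one or two missing forms can change the reported percentages noticeably.

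**Working it through.** **The plan's own figure.** Inputs are "A total sample of 10 paediatric outpatients stratified by the age groups" and "The sample estimation is calculated based on a minimum of 8 repeated measures per child", both in Respiratory Rate Comparison. The precision basis of N = 10 cannot be reproduced, because no standard deviation, within-child correlation or confidence level is given. Only the loss arithmetic can be checked:

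- Data loss: 10 resting minutes at one reading per minute × (1 − 0.20) = 8 readings, which matches the stated minimum per child.
- Attrition, if 10 is the number enrolled: 10 × 0.20 = 2 lost and 8 remaining.
- Attrition, if 10 is the number completing: 10 / 0.80 = 12.5, so 13 enrolled and 3 lost.

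The text does not settle which reading is meant. The first is the main case here.

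**Chance that the gap matters.** If each of 10 children stops independently with probability 0.20 (an assumption), the chance that nobody stops is 0.8^10 = 0.107. At least one family would fall in the gap with probability 1 − 0.107 = 0.893.

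**Size of the bias.** Let x be the number of favourable answers to one item among 8 respondents, and f (0, 1 or 2) the number of favourable answers the 2 unasked families would have given.

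Bias = x/8 − (x + f)/10

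| x of 8 | Reported | All ten, f = 0 | All ten, f = 2 | Bias range (points) |
|---|---|---|---|---|
| 8 | 100% | 80% | 100% | 0 to +20 |
| 7 | 87.5% | 70% | 90% | −2.5 to +17.5 |
| 6 | 75% | 60% | 80% | −5 to +15 |
| 4 | 50% | 40% | 60% | −10 to +10 |

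The same quantity equals 0.20 × (favourable rate among respondents − favourable rate among those unasked). At 6/8 with f = 0 this is 0.20 × (0.75 − 0) = 0.15; with f = 2 it is 0.20 × (0.75 − 1) = −0.05. If the two groups have the same underlying rate, the expected bias is zero.

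**Other reading of N.** With 13 enrolled and 10 answering, 10/10 = 100% against 10/13 = 76.9%, an overstatement of up to 23.1 points. The size is similar.

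The favourable proportion is a device for this check. The plan defines no composite score or acceptability threshold, so the arithmetic applies to any single item dichotomised as favourable or not.

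**The case against.** A reader might infer that drop-outs are definitely not asked and that acceptability is therefore overstated. The documents support neither statement as fact.

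- **The trigger.** The sentence orders the procedures and does not say completers only. A recording that ended early could be called complete, and nothing forbids giving a departing family the form. This stands as a limit on the claim. However, withdrawal is dealt with separately and without a form, so the restrictive reading is the more natural one. Wording that staff can read both ways needs repair.
- **The 20%.** It is an allowance in the respiratory-rate sample estimate, with no cause given. Consent precedes the eligibility check, so it might include consented children later found ineligible, who never wore a device. This stands: 2 of 10 is a working figure.
- **Direction.** The bias can be zero or negative. For skin irritation, early stoppers also have shorter electrode contact. This stands: the direction is plausible but not known.
- **Other sources.** The staff form has a patient-discomfort item, and withdrawal reasons are recorded. This stands in part. Staff perception is not the patient or parent answer that objective 3 names, the staff form has no skin item, and the analysis text does not bring withdrawal reasons into the acceptability summary.
- **The cannula.** Neither form asks about it, so a reader might infer that intolerance of the reference device cannot be separated from intolerance of Aingeal. The documented withdrawal reason can hold that distinction, provided it is recorded by device.
- **Importance.** This is a descriptive summary with no test or threshold. Even 8/8 has an exact 95% interval of about 63% to 100%, which contains 80%. This limits the severity. No such interval is planned, though, so a reader of the report would see only the percentage.

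**Conclusion.** The gap is real. The only stated time for the child and parent form is the end of recording, and nothing provides for families who stop early or says how missing forms are reported. On the plan's own allowance, about 2 of 10 children may not be asked.

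If both would have answered unfavourably, an item is overstated by 15 to 20 percentage points for completer results between 6/8 and 8/8. If drop-out is unrelated to the device, the expected bias is about zero. If both would have answered favourably, it is 0 to −5 points over the same range. These figures rest on three assumptions: 10 is the number enrolled, the 20% attrition occurs after the device is fitted, and withdrawn families receive no form.

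Confidence is high that the provision is missing and moderate that it would bias the result upward. Objective 3 is affected; the heart-rate and respiratory-rate accuracy objectives are not. The change is worth making because it alters who is asked at almost no cost.

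**What to change.** In Study Design (Paediatric Out-patient Population), offer the form to every child fitted with the device, and to the parent or guardian, when the electrodes are removed, whether or not recording was completed. Electrode removal is also a better moment for the skin item: the removal procedure lists it as a separate step after switch-off, and the skin under an electrode can be seen only then.

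In Withdrawal and Discontinuation, record whether the reason relates to Aingeal or its electrodes, to the Capnostream cannula, or to neither.

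In Feedback and Demographic Analysis, report the number fitted, the number who answered, and the withdrawal reasons in those three categories beside the item summaries. Do not impute withdrawals as not acceptable. The form has six separate items and no overall score, so such a rule would be a debatable choice; showing the counts lets readers judge.

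The cost is a few lines of protocol wording and one tick-box on the withdrawal record. Some withdrawing families will decline the form, and stated acceptability may be slightly lower.

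### The Bland-Altman plan states no handling of repeated readings within a child and no confidence intervals: whole-sample limits barely move, but their precision is hidden and age-group limits can be too narrow at moderate or high within-child correlation

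*Combined protocol and SAP*

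**What the plan says.** Repeated readings are part of the design. Heart Rate Comparison: "Ten subjects will provide approximately 100 minutes (or 2 hours) of Aingeal data and approximately 100 heart rates". Respiratory Rate Comparison says the same of respiration: "Ten subjects will provide approximately 100 minutes (or 2 hours) of Aingeal data and approximately 100 respiration rates". The sample-size paragraph adds: "The sample estimation is calculated based on a minimum of 8 repeated measures per child". Its allowance for losses is worded separately as "having accounted for 20% attrition rate and 20% data loss due to signal loss, noise or time discrepancies".

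Bland Altman Analysis is the only section that says how agreement will be calculated. The two sets of counts "will be compared against each other in a pair-wise manner using the approach of Bland & Altman". The plot is then described in these terms: "this involves plotting the difference in the counts against the mean of the two absolute counts". On the limits the section says: "The 95% and 99% limits of agreement, equivalent to 2 times standard deviation (sd) and 3 sd will be plotted". On the breakdown by phase and age it says: "This process will be repeated for each portion of the test (at rest and during activity) and for each age group". The only further modelling remark is that age and sex adjustment may be considered.

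No section states a between-child variance term, a summary value per child, a mixed model, or a confidence interval for the bias or for either limit.

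**The concern.** The limits of agreement are the main result for the first two objectives, the accuracy of heart rate and the comparability of respiration rate. The most natural reading of the text, though an inference, is one SD taken over all readings in a plot. If a child's differences tend to lie on the same side, readings from that child are not independent, and the precision of the bias and of the limits depends mainly on the number of children. A plot of about 100 points without an interval then looks much firmer than 8 to 10 children can support. In an age group with two or three children, the ordinary SD can also miss part of the between-child spread, so the limits themselves may be too narrow.

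**Working it through.** **Inputs from the protocol.** Ten children; 10 minutes at rest plus 5 minutes of activity; one Aingeal value per minute; at least 8 readings per child; 20% attrition and 20% data loss; four age groups.

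**The plan's own figures.** 10 children × 10 rest minutes = 100 readings, which matches the stated total. 10 × 0.8 = 8 readings matches the stated minimum. The stated 0.7 to 1.25 breaths are 5% of 14 and 25. The sample size of 10 cannot be re-derived, because no SD of differences, within-child correlation, confidence level or formula is given.

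**Assumptions.** One-way normal model for the differences, total SD 1, ICC 0.1 / 0.2 / 0.5 / 0.8. Whole sample after losses: 10 × 0.8 = 8 children and 15 × 0.8 = 12 readings each, so N = 96. Age group: an even split gives 10/4 = 2.5 children, so two or three, with the minimum of 8 readings each.

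**Step 1: expected width of the limits.** With m readings per child and N in all, the root-mean-square of the ordinary SD is √[1 − ICC × (m − 1)/(N − 1)]. The planned half-width is 2 × SD; the true 95% half-width is 1.96. At 8 × 12 and ICC 0.5: √(1 − 0.5 × 11/95) = 0.971, and 2 × 0.971/1.96 = 0.990. For two children × 8 at ICC 0.5: √(1 − 0.5 × 7/15) = 0.876, giving 0.893.

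| Planned ÷ true half-width | ICC 0.1 | 0.2 | 0.5 | 0.8 |
|---|---|---|---|---|
| 8 children × 12 | 1.014 | 1.009 | 0.990 | 0.972 |
| 3 children × 8 | 1.005 | 0.989 | 0.940 | 0.888 |
| 2 children × 8 | 0.996 | 0.972 | 0.893 | 0.808 |

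**Step 2: information on the bias.** Effective pairs = N/[1 + (m − 1) × ICC]. At 8 × 12 and ICC 0.1: 96/2.1 = 45.7.

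| Effective pairs | ICC 0.1 | 0.2 | 0.5 | 0.8 |
|---|---|---|---|---|
| 8 × 12 = 96 readings | 46 | 30 | 15 | 10 |
| 10 × 10 = 100 readings | 53 | 36 | 18 | 12 |
| Activity only, 8 × 4 = 32 readings | 25 | 20 | 13 | 9 |

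**Step 3: half-width for the bias.** The SD of a child mean is √[ICC + (1 − ICC)/12]. A 95% t interval on 8 child means has half-width 2.365 × that SD/√8, times 0.952 for the median of the sample SD on 7 degrees of freedom. At ICC 0.1: 2.365 × 0.418/2.828 × 0.952 = 0.33. Across the range: 0.33 / 0.41 / 0.59 / 0.72 SD. Treating 96 readings as independent gives about 1.985/√96 = 0.20 SD. At ICC 0 the child-level interval is 0.23 SD, so it costs little when it is not needed.

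**Step 4: share of a new child's readings inside the planned 2 SD limits** (simulation, 40,000 data sets per setting).

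| | ICC 0 | 0.1 | 0.2 | 0.5 | 0.8 |
|---|---|---|---|---|---|
| 8 × 12 | 95.0% | 94.8% | 94.4% | 92.9% | 90.6% |
| 3 × 8 | 94% | 93% | 92% | 88% | 80% |
| 2 × 8 | 93% | 92% | 90% | 84% | 72% |

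Using between- plus within-child variance with the same multiplier of 2 adds 0.1 to 1.2 percentage points at 8 × 12. At 2 × 8 and ICC 0.8 it raises the share only from 72.0% to 77.3%.

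**The case against.** The strongest reply is that the main result hardly changes: on the figures above the whole-sample limits are nearly right whichever SD is used. That stands, and it rules out the tempting reading that the headline limits are materially biased.

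A reader might also infer that the plan commits to pooling all readings as independent. It does not say so. The pair-wise wording most directly describes matching each Aingeal value to its reference value; only the silence about repeats is documented. Likewise, the plan states no interval, so it cannot be charged with reporting one that covers too seldom.

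A third inference, that age-group limits must be too narrow whenever readings correlate, fails at ICC 0.1, where three children give limits 0.5% wide and two give limits 0.4% narrow. Material narrowing needs an ICC of about 0.5 or more, for which the documents give no evidence. The ICC may be low for heart rate, where the reference is a manual count from the same ECG. Group sizes of two or three are themselves assumed.

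The whole-sample and age-group cases also use different numbers of readings per child. This matters little: at 8 × 8 the ordinary SD is 0.989 / 0.972 / 0.955 of the true SD at ICC 0.2 / 0.5 / 0.8.

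Finally, the Conclusion describes a feasibility test, and no decision rule hangs on the limits. This caps the severity. It does not remove the point, because the stated aim is to examine validity, and a validity claim needs its precision shown.

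**Conclusion.** The point holds as a cheap improvement that should be made, and no more than that. The analysis section states neither a method for repeats nor an interval, and nothing elsewhere supplies them. Following it as written would give limits with no sign that 8 to 10 children, not 100 readings, set their precision. The loss of information on the bias is roughly a half at ICC 0.1 and about nine-tenths at ICC 0.8.

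For age groups, the narrowing is conditional on the ICC and secondary to the small number of children.

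All sizes rest on the assumed ICC range, a one-way normal model, the planned loss rates and an even split across age groups. The effect in breaths or beats cannot be determined, because no SD of differences is given. For respiration, an assumed SD of 1 breath would make the bias half-width 0.33 to 0.72 breaths; an assumed SD of 3 would make it 1.0 to 2.2. The plan's 0.7 to 1.25 breaths lies across those ranges.

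**What to change.** Add to Bland Altman Analysis:

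- For the whole-sample and phase analyses, report 95% confidence intervals for the bias and for each limit with the child as the unit: for example, a t interval on child means for the bias and a variance-component interval for the limits.
- Compute the SD for the limits from between-child plus within-child variance, keeping the plan's multipliers of 2 and 3. This changes the whole-sample limits very little.
- Keep the age-group plots but label their limits descriptive. Variance components do not rescue limits from two children.

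Centring on the mean of child means, and printing the number of children on each plot, are optional.

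The cost is a paragraph of text and a few lines of code. No new data are needed, since each child already has a unique Subject ID. The downside is that the intervals will look wide. At 8 × 12, a variance-component (MOVER) interval for the upper limit has a median upper arm of 0.61 / 0.79 / 1.33 / 1.81 SD over the ICC range. It is conservative (about 97% coverage) and already 0.44 SD at ICC 0, so part of that width is the method. Age-group limits could no longer be read as performance claims.

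### The plan equates 99% limits of agreement with 3 SD, but under a Normal model 3 SD is 99.7% and 99% is 2.58 SD

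*Combined protocol and SAP*

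**What the plan says.** Under Data Analysis and Statistical Methods, the Bland Altman Analysis section says that the two sets of counts will be "compared against each other in a pair-wise manner using the approach of Bland & Altman", by plotting differences against means. It then fixes the limits: "The 95% and 99% limits of agreement, equivalent to 2 times standard deviation (sd) and 3 sd will be plotted". The rule is not confined to one overall plot: "This process will be repeated for each portion of the test (at rest and during activity) and for each age group", for both heart rate and respiration rate.

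The amount of data is given in the two comparison sections: "approximately 100 heart rates" and "approximately 100 respiration rates", each from ten subjects. The sample-size statement assumes "a minimum of 8 repeated measures per child". No section names a distribution for the differences, a small-sample correction, or any other multiplier for the limits.

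**The concern.** The sentence makes two equivalence claims, and only one holds to ordinary rounding. Limits of agreement are the mean difference plus or minus a multiple of the SD of the differences. A percentage goes with a multiple only through a distribution, and with none named the usual reading is Normal. On that reading the second pair does not match.

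Agreement is the main analysis for the first two study questions, so the wording of the limits matters to whoever reads the results. A reader who takes limits reported as 99% at face value would think the 99% range of disagreement wider than it is. A reader who recovers the SD from them by dividing by 2.576 would get an SD 16.5% too large. An analyst who follows the label and one who follows the multiplier would draw different lines.

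**Working it through.** **Inputs.** The pairs 95% with 2 SD and 99% with 3 SD come from the Bland Altman Analysis section. About 100 pairs per parameter come from the Heart Rate and Respiratory Rate Comparison sections. The minimum of 8 measures per child comes from the Respiratory Rate Comparison section and gives 10 × 8 = 80 pairs. The Normal model is my assumption. The pair counts are used only in step 4.

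**1. The plan's own pairs.** Two-sided Normal coverage at k SD is 2Φ(k) − 1.
- k = 2: 95.45%. The stated 95% is reproduced as ordinary rounding.
- k = 3: 99.73%. The stated 99% is not reproduced. One-sided coverage, Φ(3) = 99.87%, does not reproduce it either.

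**2. Multipliers that match the labels.** z(0.975) = 1.960 and z(0.995) = 2.576.
- 2 / 1.960 = 1.020, so 2 SD is 2.0% wider than an exact 95% limit.
- 3 / 2.576 = 1.165, so 3 SD is 16.5% wider than an exact 99% limit.
- Under Normality the 99% limits are 2.576 / 1.960 = 1.31 times as wide as the 95% limits. The plan makes them 3 / 2 = 1.5 times as wide.

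**3. Nominal share outside the lines.** At 3 SD it is 0.27%, or 1 in 370. The label implies 1%, or 1 in 100, which is 0.01 / 0.0027 = 3.7 times as many. Per 100 pairs that is 0.27 expected outside against 1.0.

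**4. Could a small-sample multiplier explain 3 SD?** Treating pairs as independent, the prediction-interval multiplier is t(n − 1) × √(1 + 1/n).

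| n pairs | 99% t | 99% prediction | 95% prediction |
|---|---|---|---|
| 100 | 2.626 | 2.640 | 1.994 |
| 80 | 2.640 | 2.656 | 2.003 |
| 20 | 2.861 | 2.932 | 2.145 |
| 16 | 2.947 | 3.037 | 2.197 |

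At 80 to 100 pairs neither 99% multiplier approaches 3. At 16 to 20 pairs the 99% prediction multiplier is close to 3, but the 95% multiplier is then 2.14 to 2.20, so the other half of the sentence fails.

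**The case against.** The strongest case is that this is harmless shorthand. Cut to whole percents, 95.45 and 99.73 become 95 and 99, exactly the plan's labels, and on the coverage scale the gaps are only 0.45 and 0.73 percentage points. But the plan says the limits are equivalent and does not say that it truncates; rounded, 99.73 becomes 100. This softens the point without removing it.

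A heavier-tailed model could also fit both pairs: a t distribution with 6 degrees of freedom gives about 2.00 SD and 3.03 SD. The plan invokes no such model.

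The practical weight is small, and that part of the case stands. The multiplier sits in the same sentence as the label, so a reader of the plan can recover the intended line if the multiplier is taken as governing. The 3.7-fold ratio concerns less than one pair per 100. Even with independent pairs, the relative standard error of an estimated SD is about 1/√(2(n − 1)): 7% at n = 100, and 14% at n = 25 (100 pairs split evenly over four age groups, an assumption). In an age-group plot the 16.5% displacement is therefore close to one standard error of the line's own position.

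Three stronger readings are tempting, and the documents support none of them.
- A reader might infer that every figure will carry a wrong caption, and count the figures. The plan does not say how figures will be captioned. The count depends on how the repetition is read: 2 × (1 + 2 + 4) = 14 with separate phase and age-group plots, 2 × (1 + 2 × 4) = 18 if only the overall and crossed plots are drawn, and 2 × (1 + 2 + 4 + 8) = 30 if all are drawn. Nothing in the text settles this.
- A reader might infer that the label is the slip and 3 SD was intended. The sentence names both and does not show which governs.
- A reader might take 99.73% as the coverage the study will achieve. It is a nominal figure. Actual coverage depends also on clustering within ten children, for which the documents give no figure; that is a separate matter.

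**Conclusion.** The statement that 99% limits are equivalent to 3 SD is wrong as written under the Normal model. It would place limits reported as 99% at 1.165 times their proper distance from the mean difference. The statement about 95% and 2 SD is acceptable. The conclusion rests on one assumption, that the percentages refer to a Normal distribution of differences; it needs no assumption about sample size or independence.

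The point is minor. It affects the description of a secondary reference line for both parameters and their subgroups. It changes no 95% limit and bears on no criterion by which the device would be judged acceptable. Confidence in the arithmetic is high.

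**What to change.** Reword the sentence in the Bland Altman Analysis section so that label and multiplier agree, and carry the same wording into all reported limits, overall and by subgroup. Either option works:
- keep the 3 SD lines and describe them as 3 SD (about 99.7% under Normality); or
- keep the 99% label and use 2.58 SD, with 1.96 SD for 95%.

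The sponsor should choose, since the text does not show which was meant, and should name the Normal assumption in the same sentence. The cost is one line of wording. No extra data or resources are needed.
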